7.7.1 Overdose

Overdose includes only clinically symptomatic doses that are at least twice the intended dose. Any instance of overdose (suspected or confirmed and irrespective of whether or not it involved study drugs) must be communicated to the sponsor and supporting company within 24 hours and be fully documented as an SAE. Details of any signs or symptoms and their management should be recorded, including details of any antidote(s) administered.

Proprietary Information of MD Anderson

Protocol 2020-1241

19 October 2022

Cohort 1: Ovarian cancer (ER+ and/or PR+, PI3K or PTEN altered)

[figure not shown]
Cohort 2: Endometrial cancer (ER+ and/or PR+, PI3K or PTEN altered)

Cohort 3: Breast cancers (ER+ and/or PR+, PI3K or PTEN altered). This cohort will be enriched to include at least 7 patients naïve to any PI3Ki in Stage 1 and in Stage 2.

Proprietary Information of MD Anderson

Protocol 2020-1241

[figure not shown]
19 October 2022

Proprietary Information of MD Anderson

Protocol 2020-1241

[figure not shown]
19 October 2022

Proprietary Information of MD Anderson

Protocol 2020-1241

19 October 2022

8.1 Safety Analysis

All patients who received at least 1 dose of both copanlisib and fulvestrant will be included in a descriptive safety analysis. The safety profiles will be assessed through summaries of AEs, serious AEs, AEs leading to treatment discontinuation, and treatment-related death. The safety analysis will report the frequency, severity, and duration of all treatment related AEs and laboratory abnormalities, dose interruptions, dose reductions, and toxicity-related treatment discontinuation. The worst per-patient toxicity according to NCI CTCAE grade will be used. The Bayesian Beta-Binomial model will be used to quantify the statistical inference of AE rates.

The **MDACC IND Office Medical and Safety Group** will be provided with a copy of the safety and efficacy analysis when available.

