3 STUDY ENDPOINTS

3.1 Efficacy endpoints:

Radiographic tumor assessments (CT scan or MRI) will be performed by RECIST 1.1. The endpoints of efficacy assessment include:

- ORR described as the proportion of patients who achieve CR or PR by the combination therapy.
- PFS described as the time from study treatment initiation to the date of disease progression or death due to any cause. Patients without progression will be censored at the time of the last follow up.
- OS described as the time from study treatment initiation to the date of death due to any cause. Patients without progression will be censored at the time of the last follow up.

3.2 Safety endpoints:

- Incidence of AEs including but not limited to treatment-emergent AEs, serious AEs, deaths, and clinical laboratory abnormalities, as assessed by the NCI CTCAE v5.0.
- DLT is defined as any of the following adverse reaction observed during first cycle of treatment, and assessed as *possibly*, *probably* or *definitely* related to treatment with copanlisib in combination with fulvestrant. NCI CTCAE v. 5.0 will be used for grading of AEs.

- **Non-hematological AEs:**

- Grade ≥ 2 non-infectious pneumonitis
- Laboratory abnormalities meeting Hy's law criteria (AST or ALT $>3 \times$ ULN with concomitant TB $>2 \times$ ULN). (FDA 2009)
- Any \geq Grade 3 AE, except:
 - Grade 3 fatigue lasting ≤ 5 days
 - Grade 3 nausea or vomiting that has resolved to grade ≤ 2 within 3 days after standard antiemetic therapies
 - Grade 3 diarrhea that has resolved to grade ≤ 2 within 3 days after standard antidiarrheal therapies
 - Isolated laboratory findings not associated with signs or symptoms and lasting less than 3 days, including but not limited to grade 3/4 alkaline phosphatase, uric acid, amylase, and lipase elevations, and grade 3 electrolyte laboratory abnormalities hypophosphatemia, hypokalemia,

Proprietary Information of MD Anderson

Protocol 2020-1241

19 October 2022

hypocalcemia, or hypomagnesemia responsive to supplementation and grade 3/4 lymphopenia.

- Grade 3 hyperglycemia lasting ≤ 7 days

- **Hematological AEs:**

- Grade 4 neutropenia lasting ≥ 7 consecutive days
- Grade 3 and grade 4 febrile neutropenia
- Grade 4 anemia (in the absence of disease progression in bone marrow)
- Grade 3 anemia requiring blood transfusion
- Grade 4 thrombocytopenia of any duration
- Grade 3 thrombocytopenia lasting ≥ 7 consecutive days or associated with bleeding

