- **The following event is classified as a DLT:**

- If a full cycle of copanlisib (3 doses) will not be completed due to any study intervention-related AE, the AE is considered as a DLT
- A delay of over 1 week in initiating Cycle 2 of copanlisib and/or fulvestrant treatment occurs secondary to any study drug related AE, the AE will be considered a DLT
- Death not clearly attributed to underlying disease or alternative cause

Note: Allergic reactions leading to discontinuation of study interventions will not be considered as a DLT and participant will be replaced.

3.3 Exploratory endpoints:

Biomarker-based studies will be performed using tumor tissue and liquid biopsies to assess clonal evolution, and mechanisms of innate and adaptive resistance.

Tumor biopsies, if medically feasible, will be obtained at screening (within 28 days of Cycle 1, Day 1) on-treatment after fulvestrant and copanlisib administration on Cycle 2 Day 1 and at EOT. Biopsies will be optional but encouraged, especially in patients with a response or prolonged disease control. Examples of studies include identification of genomic biomarkers of response and intrinsic or adaptive resistance by whole exome, targeted NGS, and Nanostring DSP or other similar methods.

Proprietary Information of MD Anderson

Protocol 2020-1241

19 October 2022

[figure not shown]
Mandatory blood samples to isolate plasma ctDNA will be collected at pre-treatment (Day -28 to Day1 of Cycle 1), on-treatment (pre-dose -at the same time as the on treatment biopsy- on Cycle 2 Day 1 as well as at the first two restaging visits), and post-treatment at EoT.

Plasma ctDNA samples will be used to evaluate changes in ctDNA quantity and clonal evolution by selected molecular methods that may include targeted NGS, methylation sequencing, and droplet digital polymerase chain reaction.

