5 STUDY POPULATION

5.1 Patient Population

The study population will consist of subjects with selected HR+ (ER+ or/and PR+) advanced or metastatic solid tumors with PI3K (*PIK3CA*, *PIK3R1*) and/or *PTEN* alterations. Patients must have no available standard therapy known to prolong survival or are not candidates for such a therapy.

[figure not shown]

Proprietary Information of MD Anderson

Protocol 2020-1241

19 October 2022

all patients complete the first 28 days, the study will advance to Part 2 (dose expansion), provided there is no more than 1 DLT observed. Patients will be considered evaluable for Part 1 once they have completed at least 1 cycle of treatment or they experience DLTs in the first treatment cycle.

[figure not shown]

Cohort 1: Ovarian cancer (ER+ and/or PR+, PI3K or PTEN altered).

Cohort 2: Endometrial cancer (ER+ and/or PR+, PI3K or PTEN altered).

Cohort 3: Breast cancer (ER+ and/or PR+, PI3K or PTEN altered). Cohort 3 will be enriched to include at least 7 patients naïve to any PI3Ki in Stage 1 and also in Stage 2.

Patients will be considered evaluable for Part 2 once they have completed at least 2 cycles of treatment and have at least one efficacy assessment.

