7.1 Safety Parameters

7.1.1 Definition of Adverse Event

The International Council on Harmonisation (ICH) Guideline for Good Clinical Practice (GCP) E6 defines an AE as “any untoward medical occurrence in a patient, or clinical investigation patient administered a pharmaceutical product and which does not necessarily have a causal relationship with this treatment”. An AE can, therefore, be any unfavorable and unintended sign (including an abnormal laboratory finding), symptom, or disease temporally associated with the use of a medicinal product, whether or not considered related to the medicinal product.

An AE includes but is not limited to any clinically significant worsening of a patient’s preexisting condition. An abnormal laboratory finding that requires an action or intervention by the investigator, or a finding judged by the investigator to represent a change beyond the range of normal physiologic fluctuation, should be reported as an AE.

AEs may be treatment-emergent (i.e., occurring after initial receipt of investigational product) or non-treatment-emergent. A non-treatment-emergent AE is any new sign or symptom, disease, or other untoward medical events that begin after the written informed consent has been obtained, but before the patient has received the investigational product.

Elective treatment or surgery or preplanned treatment or surgery (that was scheduled prior to the patient being enrolled in the study) for a documented preexisting condition, that did not worsen from baseline, is not considered an AE (serious or non-serious). An untoward medical

Proprietary Information of MD Anderson

Protocol 2020-1241

19 October 2022

event occurring during the prescheduled elective procedure or routinely scheduled treatment should be recorded as an AE or SAE.

The term AE is used to include both SAEs and non-serious AEs.

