7.2 Adverse Event Reporting Period

All AEs, SAEs, and other reportable safety events that occur after the ICF is signed but before study treatment initiation must be reported by the investigator if the event causes the patient to be excluded from the study, or is the result of a protocol-specified intervention, including but not limited to washout or discontinuation of usual therapy, diet, or a procedure.

- The investigator must report all AEs from the time of first protocol-specific intervention through 30 days following cessation of study treatment.
- All AEs meeting serious criteria from the time of first protocol-specific intervention through 30 days following cessation of study treatment or before the initiation of a new anticancer therapy, whichever comes first, must be reported by the investigator.
- Additionally, any SAE brought to the attention of an investigator at any time outside of the period specified above must be reported immediately by the investigator if the event is considered related to the study treatment. These events must be followed until they are resolved or stabilized

Information to be reported in the description of each AE includes:

- AE (verbatim)
- Severity grade (CTCAE Grade 1–5)
- The date of onset and resolution of the AE
- Whether the AE is serious or not, where an SAE is defined as in Section **7.1.2**.
- Investigator causality assessment with respect to the study treatment (yes or no)
- Action taken with respect to the study treatment (none, temporarily interrupted, dose reduced, permanently discontinued, unknown, not applicable)

Proprietary Information of MD Anderson

Protocol 2020-1241

19 October 2022

- Outcome (not recovered/not resolved, recovered/resolved, recovering/resolving, recovered/resolved with sequelae, fatal, unknown)

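### Read literally, the Section 8.1 safety set requires a dose of both drugs, so a patient who stops after only one is missing from its summaries; the effect is small and possibly zero

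*Combined protocol and SAP*

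**What the plan says.** Section 8.1 sets the population in one sentence: "All patients who received at least 1 dose of both copanlisib and fulvestrant will be included in a descriptive safety analysis". The same paragraph says that this analysis will summarise AEs, serious AEs, "AEs leading to treatment discontinuation, and treatment-related death", and that AE rates will be estimated with a Bayesian beta-binomial model. The readable text contains no other safety population and no rule for a patient who received only one drug.

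The other safety provisions carry no both-drug condition:

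- Section 3.2, safety endpoint: "Incidence of AEs including but not limited to treatment-emergent AEs, serious AEs, deaths, and clinical laboratory abnormalities".
- Section 7.1.1, timing: "AEs may be treatment-emergent (i.e., occurring after initial receipt of investigational product) or non-treatment-emergent".
- Section 7.2, collection: "The investigator must report all AEs from the time of first protocol-specific intervention through 30 days following cessation of study treatment".

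Three further provisions bear on who could be affected. In Section 3.2, a DLT is a first-cycle event judged at least possibly "related to treatment with copanlisib in combination with fulvestrant", and a note adds: "Allergic reactions leading to discontinuation of study interventions will not be considered as a DLT and participant will be replaced". Section 5.1 lets the study move to Part 2 "provided there is no more than 1 DLT observed". Appendix A, footnotes j and k, puts the first dose of each drug on Cycle 1 Day 1.

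**The concern.** The condition makes membership of the safety set depend on what happens after first exposure. If a reaction to the first product ends treatment before the second is given, the patient has exactly the event that the discontinuation summary is meant to count. The same event keeps the patient out of that summary.

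Safety and tolerability of the combination is a secondary objective of Part 2 (Section 2.2), and Section 8.1 is the readable analysis that reports it. For a common AE, one missing patient hardly matters. For a rare one, the statement itself can change, from no case observed to one case. What is at stake is the completeness of a descriptive summary, not a decision rule.

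**Working it through.** The plan gives no figure on this point to reproduce, and the planned sample size is not readable. The check first sorts the ways a one-drug patient can arise, then bounds the numerical effect.

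**1. Where a one-drug patient is counted**

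| Exit after one drug | Part 1 DLT count (3.2) | 8.1 summaries, read literally |
|---|---|---|
| Part 1, non-allergic stop, at least possibly related | Yes: the copanlisib cycle is not completed because of a related AE | No |
| Part 1, death not clearly due to the disease or another cause | Yes | No |
| Part 1, allergic reaction leading to discontinuation | No; patient is replaced | No |
| Part 1, stop for an unrelated event | No | No |
| Part 2, any one-drug exit | Not applicable: the readable DLT rule governs Part 1 | No |

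Collection and reporting under Sections 7.2 and 7.6 carry no both-drug condition in any row. The residual gap in Part 1 is therefore mainly allergic and unrelated stops. In Part 2 it is any one-drug exit.

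**2. Formulas**

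Let N be the patients given at least one dose of either drug, k those given only one, x the patients with the event among the N − k given both, and e the patients with the event among the k.

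- Rate under 8.1 as written: x/(N − k).
- Rate with an any-dose set: (x + e)/N.
- Difference (as written minus any-dose): [x·k/(N − k) − e]/N, which lies between −k/N and +k/N.
- If all k were excluded because an event stopped treatment, then e = k in the discontinuation summary. The difference becomes −k(N − k − x)/[N(N − k)]. Since x cannot exceed N − k, this is never above zero.

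**3. Numbers, with k = 1**

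N, k, x and e are all assumptions. The bound 1/N is 1/30 = 3.3 points and 1/60 = 1.7 points.

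| N | x | e | As written | Any-dose | Difference (points) |
|---|---|---|---|---|---|
| 30 | 0 | 1 | 0/29 = 0.0% | 1/30 = 3.3% | −3.3 |
| 30 | 2 | 1 | 2/29 = 6.9% | 3/30 = 10.0% | −3.1 |
| 30 | 2 | 0 | 2/29 = 6.9% | 2/30 = 6.7% | +0.2 |
| 60 | 0 | 1 | 0/59 = 0.0% | 1/60 = 1.7% | −1.7 |
| 60 | 3 | 1 | 3/59 = 5.1% | 4/60 = 6.7% | −1.6 |
| 60 | 3 | 0 | 3/59 = 5.1% | 3/60 = 5.0% | +0.1 |

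If every patient receives both drugs, k = 0 and the difference is zero.

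**4. Beta-binomial model named in 8.1**

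The prior is not readable; Beta(1,1) is assumed. At N = 60, 3/59 gives a posterior mean of 4/61 = 6.6% (95% credible interval 1.8 to 13.9). The any-dose 4/60 gives 5/62 = 8.1% (2.7 to 15.9). The shift of about 1.5 points is well inside either interval.

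**The case against.** The strongest reply is that the set matches the objective. Section 2.2 asks about the combination, and patients exposed to both drugs are the ones who inform it. The affected group may also be empty. Both first doses fall on the same day, and a missed one has later scheduled occasions in Cycle 1: Days 8 and 15 for copanlisib, Day 15 for fulvestrant. Section 6.2 speaks of holding the drug deemed responsible for an AE, so a reaction to one product does not by itself exclude the other. In Part 1, the most informative exits are already DLTs. The order of the two drugs on Day 1 is not readable. Nor is most of Section 8 before 8.1, where another safety population may be defined.

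All of this stands as a limit on size. None of it changes what the 8.1 sentence says. Describing combination exposure is a good reason to keep the both-drugs view, but not to make it the only one.

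A reader might infer more, and the documents do not support it:

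- *That 8.1 contradicts Sections 3.2, 7.1.1 and 7.2.* Those sections set the endpoint, timing and collection, not the analysis set.
- *That events would go unreported.* Section 7.2 requires AE reporting, and Section 7.6 requires SAE reporting regardless of attribution. Neither refers to this set.
- *That the Part 1 decision is affected.* It rests on the DLT count.
- *That the Part 2 evaluability rule in Section 5 widens the gap.* It also requires an efficacy assessment, so it says nothing about safety reporting.
- *That toxicity in general is understated.* Outside the discontinuation case above, the shift can go either way.

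**Conclusion.** The point holds as a wording weakness with a small, possibly zero, effect. On its plain meaning, 8.1 leaves a one-drug patient out of both numerator and denominator of its summaries. A looser intent, such as one dose of the regimen, is possible, but the text does not say so. The direction is fixed only for the discontinuation summary, and only for patients excluded because an event ended treatment after the first drug. The size is at most 1/N per excluded patient, on assumed values of N. The conclusion rests on the literal reading and on no other safety population being defined in the text that is not shown. The laboratory listings in 8.1.1 cover all values and are not shown to be affected.

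**What to change.** Low priority. Reword the 8.1 sentence along these lines: *The descriptive safety analysis set comprises every patient given one or more doses of either study drug (copanlisib or fulvestrant).* Present the both-drugs subset as supplementary, with the number of patients outside it and the reason for each. Leave 8.1.1 as it is, because tying it to a set could only narrow its coverage of all laboratory values. If the part of Section 8 that is not shown defines another safety population, reconcile 8.1 with it.

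The cost is a few sentences and no new data, since Section 7.2 already collects the AEs. The downside is that a few one-drug patients may enter the denominator of a combination analysis and reported toxicity may be slightly higher; the supplementary subset makes this visible.

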4 INVESTIGATIONAL PLAN

4.1 Study Design

We propose to conduct a multi-arm, open-label, phase 2 basket trial investigating the efficacy and safety of copanlisib in combination with fulvestrant in patients with selected HR+ advanced or metastatic solid cancers, harboring PI3K or PTEN alterations including ovarian cancer (cohort 1), endometrial cancer (cohort 2), and breast cancer (cohort 3). Cohort 3 will be enriched to include at least 7 patients naïve to any PI3Ki in Stage 1 and also in Stage 2.

Proprietary Information of MD Anderson

Protocol 2020-1241

19 October 2022

and will be contacted by telephone every 12 weeks (± 14 days) for survival status until death, withdrawal of consent, or lost to follow-up.

Exploratory biomarker studies using pre-treatment, on-treatment, and post-progression tumor biopsy tissues and serially collected blood liquid biopsies will investigate clonal evolution, and mechanisms of innate and adaptive resistance.

The study will consist of a screening/baseline phase, treatment phase, safety follow-up, follow-up visits, and survival follow-up.

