7.3 Assessment of Adverse Events

All AEs and SAEs, whether reported by the patient, discovered by study personnel during questioning, or detected through a physical exam, laboratory test, or other means will be reported appropriately. Each reported AE or SAE will be described by its duration (i.e., start and end dates), regulatory seriousness criteria if applicable, suspected relationship to the study treatment (see following guidance), and actions taken.

AE Attribution:

The investigator (or physician designee) is responsible for verifying and providing source documentation for all AEs and assigning the attribution for all AEs for patients enrolled.

Attribution: The determination of whether an AE is related to a medical treatment or procedure.

To ensure consistency of AE and SAE causality assessments, investigators should apply the following general guideline:

Definite - the AE is clearly related to the investigational agent.

Probable - the AE is likely related to the investigational agent.

Possible - the AE may be related to the investigational agent.

Unlikely - The AE is doubtfully related to the investigational agent.

Unrelated - The AE is clearly NOT related to the investigational agent.

Expected AEs are those AEs that are listed or characterized in the current United States Product Insert.

Unexpected AEs are those not listed in the current IB or not identified. This includes AEs for which the specificity or severity is not consistent with the description in the IB.

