7.4.2.2 Deaths

All deaths that occur during the protocol-specified AE reporting period, regardless of attribution, will be reported to the appropriate parties. When recording a death, the event or condition that caused or contributed to the fatal outcome should be reported as the single medical concept. If the cause of death is unknown and cannot be ascertained at the time of reporting, report “Death of unknown cause”.

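### The Section 3.2 safety endpoint counts AEs and deaths without an attribution limit, but Section 8.1 names only treatment-related death and details only treatment-related AEs

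*Combined protocol and SAP*

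**What the plan says.** Section 3.2 defines the safety endpoint as "Incidence of AEs including but not limited to treatment-emergent AEs, serious AEs, deaths, and clinical laboratory abnormalities", graded by CTCAE v5.0. No relatedness condition is attached.

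Section 8.1 describes the analysis in the patients who received at least one dose of both drugs. It plans summaries of AEs and serious AEs, and the list ends with "AEs leading to treatment discontinuation, and treatment-related death". In that list, death is the only item qualified by relatedness. It goes on: "The safety analysis will report the frequency, severity, and duration of all treatment related AEs and laboratory abnormalities", together with dose interruptions, reductions and toxicity-related discontinuations. It closes with "The Bayesian Beta-Binomial model will be used to quantify the statistical inference of AE rates" and does not say whether those rates are all-cause or treatment-related.

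On data capture, Section 7.4.2.2 says "All deaths that occur during the protocol-specified AE reporting period, regardless of attribution, will be reported to the appropriate parties". Section 7.2 requires the investigator to report all AEs to 30 days after treatment stops. Section 7.4.2 adopts the NCI Phase II recording guideline set out in Table 17.

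**The concern.** A reader who follows Section 8.1 literally would produce a death summary and a detailed AE table restricted to events judged related to treatment. The endpoint they are meant to report carries no such restriction, so a report could present a treatment-related death rate as the result for an endpoint that names deaths.

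The filter matters because of who applies it and in what design. The study is a "multi-arm, open-label, phase 2 basket trial" in which every cohort receives the combination, and Section 7.3 makes the investigator or a physician designee responsible for "assigning the attribution for all AEs for patients enrolled". The visible text describes no comparator that would show the background rate of an event, so the relatedness call alone decides what enters these two outputs. Section 6.3.1.5 gives an example of where that call could be hard: serious infections, including fatal ones, occurred in 8.9% of 558 patients on copanlisib monotherapy. Deciding whether such an event in a patient with advanced cancer is due to the drug or the disease is a matter of judgement.

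Safety and tolerability is the Part 1 primary objective, alongside DLTs, and a secondary objective in Part 2.

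**Working it through.** The plan states no figure on this point, so there is nothing to reproduce. The check sets the passages side by side.

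**Step 1. Match each endpoint component to its planned output.**

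| Component | Planned output | Filtered by attribution? |
|---|---|---|
| AEs, overall | General AE summary (8.1), content not specified | No |
| AE frequency, severity, duration | Detailed reporting sentence (8.1) | Yes, related only |
| Serious AEs | Serious AE summary (8.1) | No |
| Deaths | Death item (8.1) | Yes, related only |
| Laboratory abnormalities | All values listed and tabulated with CTCAE grade (8.1.1) | No |
| AE rates | Beta-binomial model (8.1) | Not stated |

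Two rows are narrower than the endpoint and one is undefined.

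**Step 2. Is relatedness implied in Section 3.2?** No. The same section limits DLTs expressly to events possibly, probably or definitely related to the combination. It states attribution where attribution is meant, and the incidence endpoint has no such limit.

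**Step 3. Do other planned outputs supply the missing death line?** Three come close.
- A fatal AE meets the serious AE definition in Section 7.1.2, so it falls within the serious AE summary. That summary is not required to give a death count.
- OS (3.1, 8.2) counts death from any cause. It is a time-to-event efficacy measure with no on-treatment window.
- Section 7.4.2.2 sends all deaths in the reporting period to the appropriate parties. That is a reporting duty and not an analysis output.

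None of these is specified as an all-cause count of deaths on or shortly after treatment.

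**Step 4. Do other outputs supply the missing AE detail?** The general AE summary might, but its content is not specified. The sentence that does specify content is limited to related AEs. The statement that the worst per-patient grade will be used carries no attribution qualifier of its own, but it does not widen that sentence.

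**Step 5. Are the data collected?** For Grade 3 to 5 events, yes: Table 17 marks these for Phase II recording at every attribution level, including unrelated and unlikely. Deaths are covered by Section 7.4.2.2. For Grade 1 to 2 events the documents conflict: Table 17 does not mark unrelated or unlikely events for Phase II, while Section 7.2 requires all AEs to be reported. If Table 17 governs, a table of all recorded AEs still depends on attribution at the low grades.

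**Step 6. Size.** The difference between all-cause and related rates depends on the number of events and the share judged unrelated. The documents give neither for this trial, and any worked example would rest wholly on assumed inputs.

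**The case against.** The strongest reply is that this is a small wording gap in an expressly descriptive analysis. The list in Section 8.1 opens with AEs and serious AEs without a filter, fatal AEs fall among serious AEs, all laboratory values are tabulated, and every death is an event in the OS analysis. The DLT endpoint depends on relatedness by design. No decision rule in the visible text turns on the wording at issue, and parts of Section 8 are not visible in the public copy.

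Much of this stands, and it rules out three stronger readings that a reader might infer. One is that attribution filters the safety result as a whole; the unfiltered rows in the table show that it does not. Another is that the plan contains no analysis of all-cause death; OS is one. The third is that unrelated events are discarded; they are recorded at Grades 3 to 5, and what is missing is a planned detailed tabulation. Nor is the open-label design a matter of unmasked allocation, since all cohorts receive the same combination. It matters only because the person judging relatedness knows that the patient received the drugs and has no control rate for reference.

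What the reply does not remove is that Section 8.1 states a narrower rule than Section 3.2 for two outputs, and that no other visible output fills either gap.

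**Conclusion.** The point holds in a limited form. The death item and the frequency, severity and duration reporting in Section 8.1 are restricted to treatment-related events, while the Section 3.2 endpoint is not. The set used for the beta-binomial AE rates is undefined and could be chosen after the data are seen. The remaining safety outputs and the mortality analysis are not affected.

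The change should be made because it replaces a stated rule that does not estimate the endpoint, and it is cheap. It does not bear on the ORR analysis or on the DLT definition. The numerical effect cannot be estimated from the documents. The conclusion rests on the visible text of Sections 3.2, 7 and 8, and on reading the absence of a relatedness qualifier in Section 3.2 as intended, which the explicit qualifier on DLTs supports.

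**What to change.** In Section 8.1:

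1. Replace the treatment-related death item with all deaths on treatment and within 30 days of the last dose, by cause and attribution. Treatment-related deaths remain visible as one category.
2. Report frequency, worst grade and duration for all recorded treatment-emergent AEs, with treatment-related AEs as a labelled subset.
3. State that the beta-binomial AE rates use the all-attribution set, with related rates shown alongside.
4. Reconcile Table 17 with Section 7.2 on Grade 1 to 2 events judged unrelated or unlikely. Until that is done, label the all-attribution table as complete for Grades 3 to 5 only.

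The cost is a few sentences and one more table. Items 1 to 3 need no new data collection, since deaths and Grade 3 to 5 events are already captured regardless of attribution. The downside is that the headline event rates will look less favourable than rates limited to related events. Showing both sets together lets the reader see how much of the difference comes from attribution.
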